6.2 Study location

The study will be carried out in Machinga and Balaka Districts, in Southern Malawi. *Machinga District* (14.55 S, 35.40 E), located ~120 km northeast of Blantyre, is a poor rural district. Malaria transmission is intense and year-round, peaking during the rainy season (November through May). Between July 2013 and June 2014, an estimated 162,500 (1-year risk of 28%) malaria cases were reported and accounted for 24% of the total Outpatient Department (OPD) attendance (the total population of Machinga District is ~572,000 people). In 2015, malaria annual incidence was 367 cases/1,000 individuals. The use of ITNs is widespread in the district; findings from the 2015-2016 MDHS reported that 66.3% of the individuals and 80.5% of under-five children slept under an ITN in the previous night.

Balaka District (15.01° S, 35.01° E), forms a boundary with Machinga and is also a poor, rural district. Malaria is generally high in the district with intense, year-round transmission that also peaks during the rainy season. Between July 2013 and June 2014, malaria cases were accounted for 29% of the total OPD attendance (the total population of Balaka District is ~372,000 people). In 2015, malaria annual incidence was 310 cases/1,000 population. Findings from 2015-2016 MDHS indicated that 67.5% of the population and 87.3% of under-five children slept under an ITN in the previous night.

The timing for this proposal is optimal as we will be able to take advantage of the Malawi government-funded nationwide ITN distribution campaign (2018) and the RTS,S evaluation project (2019). In November 2018, Malawi undertook a country-wide bed net campaign, distributing nets to each household with a target of one net for every two people. In Machinga district, PBO nets were distributed, while neighboring Balaka District conventional pyrethroid-treated bed nets were given. About eight months later, both districts are part of the vaccination of infants and young children with the RTS,S vaccine, where children in selected clusters will receive RTS,S whilst children in some clusters of the same district would act as controls. The Malawi Ministry of Health has asked our ICEMR team, through the College of Medicine Malaria Alert Centre, to support the evaluation of RTS,S vaccination, thus providing a perfect opportunity to assess the combined effects of these interventions.

6.3 Study Population

Children whose age is between 7 and 18 months, which indicates they could receive at least 3 RTS,S doses, will be eligible to participate. Following informed consent from parents/guardians, up to two children who are 18 months but \leq 10 years of age, from the same household as the vaccine-eligible child, will also be enrolled. Only households whose families intend to stay in the area for at least six months and whose eligible children will also be expected to use an assigned health center for child vaccinations will be eligible to participate.

Inclusion/Exclusion Criteria

To be eligible for the cohort, participants must meet all the following inclusion criteria:

- Children aged 7 to 18 months of age (age-eligible for at least 3 doses of RTS,S doses)
OR being one of not more than two children living in the household of an enrolled age-eligible child and being >18 mos and ≤ 10 years of age.
- Not on cotrimoxazole prophylaxis for HIV infection
- Weight >5 kg
- Permanent residence of Health Centre (HC) catchment area
- Residence within 10 km from the HC
- Written informed consent from parent/guardian for the child to participate in the study

Non-residents of the catchment area and visitors to the study area will be excluded because the study requires follow-up for at least 6 months and access to interventions such as conventional, PBO nets and malaria vaccination.

6.3.1 Study period

We will conduct two consecutive cohort studies with 500 children in the desired age group in each arm, and we will also study up to two children >18 mos and \leq 10 years of age (anticipated one or two per household) in each household to obtain preliminary data about the impact on transmission in the household (Table 3). Children will be identified and enrolled after obtaining parental consent. They will undergo interviews and one finger-prick blood sample collection every two months for six months (2, 4, and 6 months) after enrollment. Household entomological sampling will occur during the rainy season.

Table 2: Timing of Phase 1 study visits and specimen collection

Timeline	Activity
May-November 2019	Finalizing research plan and approval by IRBs (CoM and MSU)
November 2019	Community consultation with community leaders, Staff recruitment and training, Developing practical arrangements and SOPs and developing the data management system
December 2019	Cohort recruitment
January- 2019-May2020	Cohort follow up (round 1)
May 2020-October 2020	Cohort recruitment and follow up (round 2)
November 2020-March 2021	Data analysis and assessment of Go/No-Go criteria

6.3.2 Sample size

Our sample size estimates are based on previous high and low transmission season surveys conducted during the first ICEMR (2010–2017) in areas similar to the clusters that will be selected for this study. Based on these data, we anticipate that 13%-18% of households will contain a child 7-18 months old. The risk of infection in this age group is estimated to be 21% (30% high and 20% low transmission seasons). In children \leq 10 years of age the risk of infection is estimated to be 31% (46% in the high and 32% in the low transmission seasons). The within-cluster correlation is estimated at 0.004 (0.05 in the high and 0.00 in the low transmission seasons) and 0.14 (0.22 in the high and 0.06 in the low transmission seasons) for children aged 7-18 months and \leq 10 years of age, respectively. Based on these data, by studying the 25 clusters with 20 households with a child 7-18 months per intervention arm, we will analyze 500 children aged 7-18 months and a similar or larger number of older children. For power calculations, we assumed that these proportions represented the risk of incident cases of infection.

This proposed sample size will allow us to estimate moderate effectiveness of the combined interventions (versus no intervention) with 80% power in 2-sided tests, accounting for within-cluster correlation, and with α -level of 0.05. For instance, based on the cross-sectional estimations of individual risk of malaria infection obtained at enrollment of each cohort, we will be able to

detect the effectiveness of 34% (36% and 33% when stratifying by season) in children 7-18 month-old (Hayes, 2009). In a repeated measure analysis, with within-subject correlation of 1.5 to 2 times larger than within-cluster correlation, we will be able to detect effectiveness of 34-37% in children 7-18 month old (Liu, 2002).

For entomological assessments, 100 households from each of the two arms will be visited for entomological analysis including *Anopheles* abundance, female mosquito parity, and source of blood meal and sporozoite prevalence. Based on our previous experience, we have found an average of one *Anopheles* mosquito per household sampled (although with very heterogeneous distribution), and 75-95% human-biting prevalence.

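### Does the 34-37% detectable effectiveness for the repeated-measures analysis need to be reworked because its inputs and its season are not stated?

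*Combined protocol and SAP*

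**What the plan says.** Section 6.3.2 plans 25 clusters of 20 households per arm, giving 500 children aged 7-18 months, with 80% power and a two-sided 5% level. The control risk is 21% overall, 30% in the high season and 20% in the low season. On clustering: "The within-cluster correlation is estimated at 0.004 (0.05 in the high and 0.00 in the low transmission seasons". The survey proportions are then treated as incident risks: "For power calculations, we assumed that these proportions represented the risk of incident cases of infection".

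Two detectable effects follow. For a single survey the study can "detect the effectiveness of 34% (36% and 33% when stratifying by season) in children 7-18 month-old". For repeated measures, "with within-subject correlation of 1.5 to 2 times larger than within-cluster correlation, we will be able to detect effectiveness of 34-37" per cent, with a literature citation and no seasonal split.

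Section 6.3.1 describes the follow-up: "We will conduct two consecutive cohort studies with 500 children in the desired age group in each arm", sampled "every two months for six months (2, 4, and 6 months) after enrollment". Table 2 recruits round 1 in December 2019 and follows it to May 2020. Section 6.2 describes transmission as "peaking during the rainy season (November through May".

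For children up to 10 years, Section 6.3.2 says "the risk of infection is estimated to be 31% (46% in the high and 32% in the low transmission seasons".

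**The concern.** The repeated-measures figure is the one closest to the planned primary models in Section 6.5, which account for correlation across time. Its only stated parameter is the 1.5-2 ratio of within-subject to within-cluster correlation. The low-season correlation is 0.00, so that ratio makes the within-subject correlation zero there.

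The pooled inputs also sit almost on the low-season values. The implied high-season weight is (21 - 20)/(30 - 20) = 10% for the risk and 0.004/0.05 = 8% for the correlation, yet one of two equal cohorts lies inside the transmission peak. If the range describes only low-season conditions, a reader could overrate what round 1 can detect. Section 6.1 makes the application for a larger study depend on significant results, so that would matter.

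Two further slips add to the doubt. The pooled 31% for children up to 10 years is below both of its seasonal values. The number of time points also varies: six for the younger children and four for household members in Section 6.5, with monthly visits mentioned in Section 7.3.1.

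**Working it through.** **Inputs.** From Section 6.3.2: 500 children per arm, clusters of 20, two-sided 0.05, 80% power; risk and intracluster correlation (ICC) of 21%/0.004 pooled, 30%/0.05 high season, 20%/0.00 low season. The test is an unpooled comparison of two proportions, solved for the effectiveness that gives 80% power.

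**Step 1: the plan's single-survey figures.** Effective size per arm is 500/(1 + 19 × ICC).

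| Inputs | Effective n per arm | Detectable | Plan |
|---|---|---|---|
| Pooled | 500/1.076 = 464.7 | 33.1% | 34% |
| High season | 500/1.95 = 256.4 | 35.3% | 36% |
| Low season | 500/1 = 500 | 32.9% | 33% |

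All three agree to within 0.9 point. With a pooled-variance test, power at the stated 34%, 36% and 33% is 81.9%, 81.2% and 80.0%.

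**Step 2: repeated measures.** The cited method is not in the documents, so these design effects are my assumptions. With T visits and within-subject correlation r of 1.5 to 2 times the ICC:

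- A, cluster correlation only within a visit: n = 500T/(1 + (T - 1)r + 19 × ICC).
- B, cluster correlation fully persistent: n = 500T/(1 + (T - 1)r + 19 × T × ICC).

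The risk p is read either as the risk at each visit, or as cumulative over follow-up with per-interval risk 1 - (1 - p)^(1/T). The ICC is kept unchanged at that lower risk, which is also an assumption. For example, pooled inputs with T = 4 give 1 - 0.79^(1/4) = 0.0572. With r = 0.008, A gives n = 2000/(1 + 0.024 + 0.076) = 1818 and 34.45%; B gives n = 2000/(1 + 0.024 + 0.304) = 1506 and 37.51%.

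| Inputs | T | Cumulative, A | Cumulative, B | Per visit, A to B |
|---|---|---|---|---|
| Pooled | 3 | 34.2% | 36.3% | 19.9-21.2% |
| Pooled | 4 | 34.4-34.5% | 37.4-37.5% | 17.4-19.1% |
| Low | 3 | 33.7% | 33.7% | 19.6% |
| Low | 4 | 33.8% | 33.8% | 17.1% |
| High | 3 | 37.9-38.3% | 50.3-50.6% | 21.8-29.8% |
| High | 4 | 38.7-39.3% | 55.7-56.0% | 19.3-29.0% |

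The stated 34-37% matches the pooled cumulative rows (34.2-37.5%). The per-visit reading gives much smaller detectable effects, so on that reading the stated range is conservative.

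**Step 3: could the range already span the seasons?** Under A with cumulative risk, low to high season runs from 33.5% to 36.9-37.2% at T = 2, and from 33.7% to 37.9-38.3% at T = 3. T = 2 is not the planned schedule, and T = 3 overshoots by about 1 point. The single-survey figures also differ by up to 0.9 point, so this reading cannot be ruled out.

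**Step 4: the 1.5-2 ratio.** It moves the pooled cumulative result by 0.05-0.09 point at T = 3-4, so on pooled inputs it does not explain a 3-point range. On high-season inputs under A it moves the result by 38.31 - 37.90 = 0.4 point (T = 3) or 39.28 - 38.69 = 0.6 point (T = 4).

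**Step 5: the slips.** A pooled 31% would need a high-season weight of (31 - 32)/(46 - 32) = -7%, which is impossible. Every detectable effect in Section 6.3.2 is for children aged 7-18 months, so none uses the 31%. On visits, the Executive Summary, Section 6.1, Section 6.3.1, Table 3 with its text, and Section 7.3.2 all describe enrollment followed by two-monthly sampling to month 6.

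**The case for a change.** The strongest case for a change is that the missing inputs matter numerically. At 3-4 visits the plan's own risks and correlations give anything from about 17% to 56%, and only an unstated cumulative reading lands on 34-37%. On that reading the high season lies above the range (37.9-39.3% under A, 50.3-56.0% under B). With six time points the pooled figure under B would be 39.6-39.7%, outside the range. Writing the inputs down would take one paragraph.

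What stands is that the range is under-documented and the repeated-measures figure has no explicit seasonal split. What does not stand is that the high-season figure is worse than 37%. The 50-56% values need cumulative risk, full persistence of cluster correlation between visits, and an ICC of 0.05 carried unchanged to a per-interval risk of about 9-11%. The per-visit reading of the same inputs gives 19-30%. Nothing in the documents favours the unfavourable set. Part of the difficulty in checking the range is also that the cited method is not to hand. The plan does give a seasonal split for the single survey, and its 36% already tells the reader that round 1 needs a somewhat larger effect.

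**Conclusion.** The concern is correct about what Section 6.3.2 omits, but it does not show a wrong number, a missed power claim or an inadequate sample size. The single-survey figures reproduce to within 0.9 point. The 34-37% agrees with pooled inputs, cumulative risk and 3-4 visits (34.2-37.5%), and is conservative if the risk applies at each visit (17.4-21.2%). Whether the high-season value is better or worse than 37% is not established: about 19-30% per visit, 38-56% cumulative. These results rest on assumed design effects in place of the cited method.

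The range is a planning statement for a preliminary cohort. The 25 × 20 layout stands whichever reading is right, and no analysis or decision rule in the plan uses 34-37%. The random-effects models of Section 6.5 will estimate the correlations from the data, and the precision achieved in each season will show in the results. Analysts will work from the data at enrollment and months 2, 4 and 6, whatever the stray wording about six time points or monthly visits. The 31% is a clerical error with no effect on any stated detectable effect. Spelling out the inputs would make the paragraph tidier and would alter no result.

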6.4 Participant recruitment and study procedures

Participant recruitment. Prior to recruiting participants, households in which children have received RTS,S and PBO nets will be identified. (PBO+, RTS,S+). Additionally, through vaccination records, we will identify households in Balaka where children who received the full scheme of Pentavalent (Diphtheria-pertussis-tetanus; Hepatitis B; Haemophilus influenzae type b) vaccine and have received a standard bed net live. In Nyambi catchment area, by the end of September, an estimated 260 children are expected to be vaccinated with RTSS vaccine. Thus, to achieve an adequate sample size for the significant inferential statistics, children will be enrolled from the Health Centre and tracked back in the community. Children will be identified and RTS,S information will be extracted from the registers by the research team. With the help from the health surveillances Assistants (HSAs) and community health volunteers (CHVs), RTS,S age-eligible children (7-18 months old) will be tracked using information obtained from the registers back to their villages and households where children will be enrolled and followed up for the designated study period. In the Kalembo catchment area, the same process that will be employed in Nyambi will be adopted. However, to make the cohort more comparable, using under two EPI vaccine register, children who completed three doses of Pentavalent (Diphtheria-pertussis-tetanus; Hepatitis B; Haemophilus influenzae type b) vaccine and are in RTS,S vaccine age-eligible will be considered in Kalembo.

In both catchment areas, up to two children in the household aged >18 months and \leq 10 years old residing with the vaccine age-eligible children will also be offered the opportunity to enroll. All invited children will be screened by a study nurse for eligibility using a screening form. During the screening process, the details of the study procedures that will take place in the cohort will be described in detail. For children who meet the eligibility criteria, parents/guardians will then be asked whether they are willing to have their child participate in the study and those that agree will be asked to sign the consent form. A copy of the signed consent form will be given to the head of the parent/guardian. All enrolled will be given a study identification number. Only children from the families intending to stay in the area whose parents provide written informed parental consent will be considered for enrollment. In addition, consent will be sought from the parent/guardian for entomological activities in the household.

Table 3: Overview of study procedures

Visit Type	Home Visit/enrollment	Two-monthly visits: Central location near home
Study procedure		
Potentially eligible participants identified through satellite imagery and predetermined clusters. Households are visited and those with eligible children identified	X	
Obtain informed consent to participate in the study	X	
Child demographic and HH socioeconomic information	X	
Through a finger prick, collect blood sample and DBS for quantitative PCR, serum separation, antibody quantification, preservation of RNA, and storage – done on every two months follow up for entire 6 months.	X	X
Structured questionnaire interview	X	X
ITN use and vaccination status	X	X
Participants reminded of their visit date	X	X
Household mosquito collection for testing		One time
Hemoglobin measurement	X	X
Malaria rapid diagnostic test	X	Final visit only

At enrollment, we will conduct household and individual interviews. In this initial household interview, we will collect data on hemoglobin status, SES, household construction, and on ITN use (PBO or conventional net). Through visual inspection of each bed net to determine if it is a PBO or conventional net, we will also identify which other household members aged ≤ 10 years of age who slept under each bed net and with respective frequency. We will also document vaccination status including RTS,S vaccine administrations. See details of proposed study procedures at the enrollment and every two months follow up for six months in the community. See Table 3 above.

Individual participant's visits. Every two months through the sixth month, participants in the cohort will be invited to the nearest central location for data and specimen collection. A structured questionnaire will be administered to collect information on demographics, net utilization and vaccination status). At each visit, we will review the target child's health passport to document all vaccinations, including the standard EPI vaccines through 9 months of age and the 15-month measles vaccine. We will also document the dates of all RTS,S vaccine administrations.

Human blood samples and testing.

Clinical testing: To establish the study cohort, potential participants will be screened by the study team to assess for their eligibility. At enrollment the cohort will be screened for malaria using Malaria Rapid Diagnostic Tests (The SD BIOLINE Malaria Ag P.f/Pan (HRP-II)™ rapid diagnostic test RDT) and those participants who test positive will be treated with a full, weight appropriate treatment course of dispersible artemether-lumefantrine (LA) by government Staff. The RDT and treatment of RDT positive children will be repeated at the final visit.

Hemoglobin levels from each participant will also be examined at enrollment and at every two-month follow-up visits. Parents of children with a haemoglobin level under 11 g/dl will be advised to take the child to a health facility for follow-up care and will be given a referral letter with the haemoglobin reading to show to staff at the health facility by the research Team.

Molecular analyses: At enrollment and at every two-month visit, we will collect finger-prick blood samples from all enrolled participants. These specimens will be used to assess *P. falciparum* infection by quantitative PCR. Then the specimens will be stored for later determination of gametocyte-specific gene expression and gametocyte density. Serum will be collected to assess for serological evidence of exposure to infection and response to vaccination.

Household mosquito collection and testing. Vector populations will be sampled from 100 study households (from RTS,S age-eligible households) in both intervention arms. The selection of the households for mosquito collection will be done during the recruitment of age-eligible children. In each catchment area CDC miniature light traps will be set in sleeping rooms to capture host-seeking vectors indoors. We will also sample blood-fed and gravid mosquitoes by indoor aspiration and exit trap sampling. Sampling will occur at each house on four consecutive nights during the last four weeks of the rainy season to optimize catch numbers. Light traps will be set up in a single functional bedroom in each of the households. Local personnel in each catchment area will be trained to carry out these procedures.

Species of captured adult mosquitoes will be determined by visual examination under microscopy and PCR-based assays using procedures well established in our laboratories. Blood-fed mosquito abdomens will be tested for the host species that were fed upon using a PCR method based on the vertebrate mitochondrial cytochrome B gene. The separated thorax and head of each female will be tested for salivary gland *P. falciparum* sporozoites using standard ELISA or PCR to estimate infection prevalence. For non-blood fed mosquitoes, we will assess their parity status by dissection and examination of mosquito ovaries.

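### Entry rules are inconsistent between sections and partly arm-specific, which creates a risk of differential selection between Nyambi and Kalembo

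*Combined protocol and SAP*

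**What the plan says.** Section 6.4 describes recruitment by arm. For the intervention group, "households in which children have received RTS,S and PBO nets will be identified"; the number of RTS,S doses is not stated. For Balaka, it looks for households with a child who has had the full pentavalent schedule "and have received a standard bed net live". It then says: "In the Kalembo catchment area, the same process that will be employed in Nyambi will be adopted". A qualification follows for Kalembo only: "to make the cohort more comparable, using under two EPI vaccine register, children who completed three doses of Pentavalent".

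The same section also says that "RTS,S age-eligible children (7-18 months old) will be tracked using information obtained from the registers", which describes age eligibility and not receipt. Table 3, in the same section, has another frame: "Potentially eligible participants identified through satellite imagery and predetermined clusters", followed by household visits. Section 6.3.2 bases power on "25 clusters with 20 households with a child 7-18 months per intervention arm".

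Elsewhere, the executive summary compares households according to whether they are due to get the interventions. Section 6.1 builds the cohorts from registers of age-eligible children. The inclusion criteria in Section 6.3 require age eligibility, with no condition on RTS,S, nets or pentavalent. Section 6.5 plans to compare children who do and do not comply with RTS,S, PBO nets or both.

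**The concern.** Section 6.1 describes a prospective cohort with one health centre per arm. Randomisation does not balance the children who enter, so the contrast depends on the two groups being drawn in the same way. Completing a vaccine schedule plausibly goes with care-seeking, access and net use, all of which may relate to infection risk. If Nyambi children enter because they took up RTS,S and Kalembo children because they completed pentavalent, the groups may differ in these respects before any effect of the interventions.

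A second difficulty is that recruitment staff cannot follow all of this text at once. A register reaches only children who have attended; a satellite-based household search also reaches those who never did. Section 6.1 makes significant results here the trigger for applying to fund a much larger study, so a distorted contrast could mislead that decision.

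**Working it through.** **1. The entry rules side by side**

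| Place | Frame | Condition for the 7-18 month child |
|---|---|---|
| Executive summary | not stated | household due to get both interventions, or neither |
| 6.1 | malaria and vaccine registers | age-eligible |
| 6.3 criteria | not stated | age-eligible; no vaccine or net condition |
| 6.4, Nyambi | health-centre register, traced to home | RTS,S and PBO net received (opening) or age-eligible (later) |
| 6.4, Kalembo | under-two EPI register, traced to home | age-eligible, three pentavalent doses, standard net received |
| 6.4, Table 3 | satellite imagery, predetermined clusters, home visits | not arm-specific |
| 6.5 | not stated | expects both compliers and non-compliers |

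The net rule runs in parallel across arms. The vaccine rule does not: pentavalent completion is stated for Kalembo only. If RTS,S receipt were an entry condition, Nyambi would have no RTS,S non-recipients for the comparison in 6.5.

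**2. The plan's own benchmark**

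Inputs from 6.3.2: 500 children per arm as 25 × 20; control risk 21% (30% high season, 20% low); within-cluster correlation (ICC) 0.004 (0.05, 0.00); 80% power; two-sided 0.05. Design effect = 1 + (20 − 1) × ICC; effective n per arm = 500 / design effect. A two-proportion test with pooled variance is solved for 80% power.

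- Overall: design effect 1.076, effective n 464.7, detectable effectiveness 33.2% (plan: 34%).
- High season: 1.95, 256.4, 35.5% (plan: 36%).
- Low season: 1.00, 500, 33.0% (plan: 33%).

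The plan's figures reproduce, so they are a sound yardstick.

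**3. What a selection difference would do**

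The documents give no figure for it, so the ratios here are assumed. Take no true effect, control risk 21%, ICC 0.004 and 500 per arm, and let R be the risk ratio between the groups due to selection alone. Apparent effectiveness is 1 − R.

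| R | Apparent effectiveness | Two-sided 5% test rejects |
|---|---|---|
| 0.95 | 5% | 6.8% |
| 0.90 | 10% | 12.6% |
| 0.80 | 20% | 37% |
| 0.70 | 30% | 71% |

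R above 1 works the other way. Suppose pentavalent completion goes with 20% lower risk, and a fraction f of Nyambi recruits have completed it against all in Kalembo (both assumed). The risk ratio is then multiplied by f + (1 − f)/0.8:

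- f = 0.9: 0.9 + 0.1/0.8 = 1.025
- f = 0.7: 0.7 + 0.3/0.8 = 1.075

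A true ratio of 0.66 becomes 0.66 × 1.025 = 0.68 or 0.66 × 1.075 = 0.71, so 34% effectiveness would read as about 32% or 29%. If RTS,S takers use services more than pentavalent completers do, R falls below 1 instead. Neither direction can be excluded.

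**4. If RTS,S receipt is required in Nyambi**

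Section 6.4 expects about 260 children vaccinated there by the end of September, against a target of 500. With 260 in Nyambi (risk 0.21 × 0.66 = 0.1386) and 500 in Kalembo (0.21), dividing by 1.076 gives effective sizes of 241.6 and 464.7.

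- Pooled risk = (464.7 × 0.21 + 241.6 × 0.1386) / 706.3 = 0.1856.
- Null standard error = √[0.1856 × 0.8144 × (1/464.7 + 1/241.6)] = 0.0308.
- Alternative standard error = √[0.21 × 0.79/464.7 + 0.1386 × 0.8614/241.6] = 0.0292.
- Power = Φ[(0.0714 − 1.96 × 0.0308)/0.0292] = about 65%.

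With 260 in each arm it is about 54%. This is a lower-end case, because Table 2 puts the first recruitment in December 2019 and a second round from May 2020, so more children could be vaccinated by then.

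**The case against.** The strongest reply is that no RTS,S is given in the Kalembo arm, so some proxy for use of vaccination services is needed there. Pentavalent completion is that proxy and is adopted explicitly for comparability. This stands: compared with unrestricted controls, it probably removes some bias. What remains is that the rule is not stated for Nyambi, and RTS,S receipt with no dose count may not select an equivalent group.

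A reader might infer that the plan builds selection bias into the comparison. The documents do not support that. Four places (the executive summary, 6.3, the later text of 6.4, and 6.5) leave open whether RTS,S receipt is an entry condition at all. Kalembo also has a net rule, and Section 6.4 says the tracing process is the same in both areas. Table 3 applies to both arms, so it is a contradiction to resolve and not itself a difference between them.

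A reader might also infer a material loss of precision from unequal village sizes under register tracing. That is a separate matter, and small at the plan's overall ICC: with an assumed coefficient of variation of 0.6, the design effect is 1 + (1.36 × 20 − 1) × 0.004 = 1.105 against 1.076, so intervals are √(1.105/1.076) = 1.013 times as wide. At the low-season ICC of zero there is no change. Nor does register tracing rule out sampling by cluster.

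Finally, Section 6.4 already records EPI vaccines and RTS,S dates from the health passport, along with socioeconomic data and net use. Section 6.5 plans baseline comparisons to look for selection bias and will explore causal models for adherence. These help, but the models are exploratory and concern adherence among enrolled children. They cannot recover children whom an unequal entry rule left out.

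**Conclusion.** The point holds as a risk. The entry rules and frames conflict, and the vaccine condition as written differs between arms. In a non-randomised comparison of one health centre per arm, this opens the way to differential selection of unknown direction and size. The rejection rates and the shifts in effectiveness shown above rest on assumed inputs; they show how much could turn on the entry rule and do not estimate the bias. The power figures of about 65% and 54% apply only if RTS,S receipt is required and the Nyambi pool stays at 260. The text should be changed, because the remedy is specific and costs little. The documents do not show that the comparison is already biased.

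**What to change.** Use one frame, the under-two EPI register, in both catchments. Use one entry rule in both: age-eligible, three pentavalent doses, and a net received in the campaign. Treat number of RTS,S doses and net type, already collected under Section 6.4, as exposure and not as entry conditions, so that the Nyambi pool is not limited to RTS,S recipients. Bring the executive summary, 6.3, 6.4 (including the first row of Table 3) and 6.5 into line with this rule. If children already enrolled in Nyambi lack three pentavalent doses, restrict or adjust on pentavalent status from the health passport.

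The cost is protocol wording, one more register check in Nyambi, and the exclusion of children there without three pentavalent doses. That loss would not clearly be small if RTS,S receipt were also required: at an assumed 10-30% without full pentavalent, it is 26 to 78 of 260. Without that requirement the pool is wider. The catchment contrast would then describe the interventions at the uptake actually achieved, and effects in recipients would need the adjusted analyses of 6.5.
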